5.6 Expected Duration of Each Subject's Participation

Three (3) Years

5.7 Number of Subjects Required to be Included in the Clinical Investigation

At least 85 subjects will be enrolled and undergo the TVRS procedure to obtain 85 analysis subjects (i.e., subjects who will be included in the analysis of endpoints).

5.9 Trial Completion

A Trial Completion eCRF must be completed for each patient when:

- the subject is considered lost to follow-up per the above definition or
- the subject withdraws from the Trial or
- the subject is withdrawn due to screen failure or
- the investigator withdraws the subject from the trial or
- the subject dies or
- the subject completes the Trial (e.g., 3 year follow-up time point has been reached) or
- the sponsor terminates the Trial.

Sponsor must be notified of the reason for subject discontinuation. The site will provide this information on the eCRF. Investigators must also report this to their EC/IRB as defined by their institution's procedure. Subjects will not be replaced.

(Version 2.0; 01 February 2018)

6.0 TREATMENT AND EVALUATION OF THE TVRS

After patients successfully completed screening, the subsequent visits will be performed in the following order: Baseline, Index Procedure, Discharge, 30 day, 6 months, 1 year, 2 years and 3 years visits. Details are provided below.

6.1 Baseline Clinical Assessments

a baseline visit must be completed (may occur on the day of, but prior to the TVRS procedure). Per **Table 2: Clinical Evaluation Schedule**, clinical assessments at baseline include medical history, weight, temperature, heart rate, blood pressure, the Short Form Health Survey (SF-36) Quality of Life (QoL) questionnaire, Kansas City Cardiomyopathy Questionnaire (KCCQ), New York Heart Association (NYHA) Functional Class, Six Minute Walk Test (6MWT) distance, blood test (includes BNP or NT-ProBNP, CK or CK-MB, blood urea nitrogen, serum creatinine, and AST or ALT) and medical history assessments. History of heart failure hospitalizations in the prior 1-year will be collected as part of the medical history at the baseline visit. Concomitant cardiovascular medications, including dosage, will also be collected at this visit.

A 12-lead ECG must be performed within 24 hours prior to the TVRS procedure to rule out an acute myocardial infarction (**Table 2: Clinical Evaluation Schedule**).

[figure not shown]

[figure not shown]

[figure not shown]

(Version 2.0; 01 February 2018)

³² Nishimura, et al. ACC/AHA 2008 Guideline Update on Valvular Heart Disease: Focused Update on Infective Endocarditas: A Report of the American College of Cardiology/American Heart Association Task Force on Practice Guidelines: Endorsed by the Society of Cardiovascular Anesthesiologists, Society for Cardiovascular Angiography and Interventions, and Society of Thoracic Surgeons. *Circulation* 2008; 118(8):887-894.

(Version 2.0; 01 February 2018)

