 - Subcategories confirmed by autopsy or imaging or lumbar puncture
 - Intraocular bleed compromising vision
- Type 4: CV Surgery-related bleeding

³³ Mehrana R, Rao SV, et al. Standardized bleeding definitions for cardiovascular clinical trials: a consensus report from the Bleeding Academic Research Consortium. *Circulation* 2011;123:2736-2747.

(Version 2.0; 01 February 2018)

- o Perioperative intracranial bleeding within 48 h
- o Reoperation after closure of sternotomy for the purpose of controlling bleeding
- o Transfusion of ≥5 U whole blood or packed red blood cells within a 48-h period†
- o Chest tube output ≥2L within a 24-h period
- Type 5: Fatal bleeding
 - o Type 5a
 - Probable fatal bleeding; no autopsy or imaging confirmation but clinically suspicious
 - Type 5b
 - Definite fatal bleeding; overt bleeding or autopsy or imaging confirmation
- *Corrected for transfusion (1 U packed red blood cells or 1 U whole blood=1 g/dL hemoglobin)
- †Cell saver products are not counted

MAJOR VASCULAR COMPLICATION

Any major complication, relating to, or affecting, the circulatory system as a result of the TVRS procedure, including new onset of any of the following:

- Hematoma at access site >6 cm.;
- Retroperitoneal hematoma;
- Arterio-venous fistula;
- Symptomatic peripheral ischemia/ nerve injury with clinical signs or symptoms lasting >24 hours;
- Vascular surgical repair at catheter access sites;
- · Pulmonary embolism;
- Ipsilateral deep vein thrombus; or
- Access site-related infection requiring intravenous antibiotics and/or extended hospitalization.

MODIFIED RANKIN SCALE SCORE DESCRIPTIONS

- 0. No symptoms at all
- 1. No significant disability despite symptoms; able to carry out all usual duties and activities
- 2. Slight disability; unable to carry out all previous activities, but able to look after own affairs without assistance
- 3. Moderate disability; requiring some help, but able to walk without assistance
- 4. Moderately severe disability; unable to walk without assistance and unable to attend to own bodily needs without assistance
- 5. Severe disability; bedridden, incontinent and requiring constant nursing care and attention
- 6. Dead

MYOCARDIAL INFARCTION

Myocardial infarction (MI) classification and criteria for diagnosis is defined as follows:

Peri-procedural MI (≤ 72 hours after TVRS procedure)

Mandatory: CK-MB (preferred) ≥10x ULN within 72 hrs. post-TVRS procedure in patient with normal baseline CK-MB

OR

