Mandatory: CK-MB ≥5x ULN within 72 hrs. post-TVRS procedure in patient with normal baseline CK-MB *plus* new pathological Q-waves in ≥2 contiguous leads, or new LBBB

Post-surgery

Mandatory: CK-MB ≥10x ULN (preferred) within 24 hrs. of cardiothoracic surgery *plus 1 of the following:*

(Version 2.0; 01 February 2018)

- New pathological Q-waves in ≥2 contiguous leads or new persistent LBBB on ECG ≥30 min. and ≤72 hrs. post-CABG cardiothoracic surgery, or
- New substantial wall motion abnormalities by imaging except new septal or apical abnormalities.

Spontaneous MI (>72 hours after TVRS procedure)

Any one of the following criteria:

- Detection of rise and/or fall of cardiac biomarkers (CK-MB) with at least one value above the upper limits of normal (ULN), together with evidence of myocardial ischemia with at least one of the following:
 - ECG changes indicative of new ischemia [new ST-T changes or new left bundle branch block (LBBB)]
 - o New pathological Q waves in at least two contiguous leads
 - Imaging evidence of new loss of viable myocardium or new wall motion abnormality
- Sudden, unexpected cardiac death, involving cardiac arrest, often with symptoms suggestive of myocardial ischemia, and accompanied by presumably new ST elevation, or new LBBB, and/or evidence of fresh thrombus by coronary angiography and/or at autopsy, but death occurring before blood samples could be obtained, or at a time before the appearance of cardiac biomarkers in the blood.
- Pathological findings of an acute myocardial infarction.

NEW YORK HEART ASSOCIATION CLASSIFICATION (NYHA CLASS)

Class I	Patients with cardiac disease but without resulting limitations of physical activity.		
Class II	Patients with cardiac disease resulting in slight limitation of physical activity. Patients are comfortable at rest. Ordinary physical activity results in fatigue, palpitation, dyspnea, or anginal pain.		
Class III	Patients with cardiac disease resulting in marked limitation of physical activity. Patients are comfortable at rest. Less than ordinary physical activity causes fatigue, palpitation dyspnea, or anginal pain.		
Class IV	Patients with cardiac disease resulting in inability to carry on any physical activity without discomfort. Symptoms of cardiac insufficiency or of the anginal syndrome may be present even at rest. If any physical activity is undertaken, discomfort is increased.		

NON-ELECTIVE (i.e., URGENT or EMERGENT) CARDIOVASCULAR SURGERY FOR DEVICE RELATED EVENTS

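### Section 6.1 accepts total CK alone at baseline, but both peri-procedural MI criteria need a normal baseline CK-MB, so peri-procedural MI cannot be ascertained as defined in CK-only subjects

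*Protocol*

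**What the plan says.** Protocol Section 6.1 describes the baseline assessments, by reference to Table 2, and includes "BNP or NT-ProBNP, CK or CK-MB" in the blood test. Either marker satisfies the requirement.

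The MI definition in Protocol Appendix II has three parts.

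- **Peri-procedural (72 hours or less after the procedure).** There are two alternative routes, each marked mandatory. The first is "CK-MB (preferred) ≥10x ULN within 72 hrs. post-TVRS procedure in patient with normal baseline CK-MB". The second is "CK-MB ≥5x ULN within 72 hrs. post-TVRS procedure in patient with normal baseline CK-MB", together with "new pathological Q-waves in ≥2 contiguous leads, or new LBBB".
- **Post-surgery.** A CK-MB threshold applies "within 24 hrs. of cardiothoracic surgery", with supporting ECG or imaging evidence. No baseline value is required.
- **Spontaneous (more than 72 hours after the procedure).** This is met by "Any one of the following criteria", and three criteria follow. Only the first uses a biomarker.

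MI is one of the components of the MAE composite (Protocol Section 4.2, SAP Section 1.3.1). The six-month MAE rate is tested against a performance goal of 39% (SAP Section 2.2.1.2). The planned number of analysis subjects is at least 85 (Protocol Section 5.7).

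**The concern.** The list of what a site must collect does not match the definition that the data must feed. A site can follow Section 6.1 exactly and still lack the one baseline value that both peri-procedural MI routes need. That window covers the procedure itself and the three days after it.

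The direction of the error matters. If the definition is applied as written, an infarction in a CK-only subject fails to qualify. The reverse error, a CK-only baseline creating an MI, cannot happen. The observed MAE rate can only fall, which favours the device. The trial is single-arm and tested against a fixed goal, so no control group shares the bias. Ascertainment would also vary between sites with the choice of assay, for reasons unrelated to the patients.

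The protocol handles a similar choice consistently elsewhere. Section 6.1 accepts AST or ALT, and the liver failure definition in Appendix II accepts either enzyme. The MI definition has no matching provision for CK.

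**Working it through.** The plan states no figure on this point that could be reproduced, so the check compares the passages. The six MI criteria in Appendix II are set against a baseline that contains CK only.

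| Criterion | When it applies | Biomarker named | Normal baseline CK-MB needed? | Blocked by a CK-only baseline? |
|---|---|---|---|---|
| Peri-procedural 1 | 72 h or less after procedure | CK-MB, 10 times ULN (*preferred*) | Yes | Yes |
| Peri-procedural 2 | 72 h or less after procedure | CK-MB, 5 times ULN, plus ECG change | Yes | Yes |
| Post-surgery | Within 24 h of cardiothoracic surgery | CK-MB, 10 times ULN (*preferred*), plus ECG or imaging | No | No |
| Spontaneous 1 | After 72 h | CK-MB above ULN, plus evidence of ischemia | No | No |
| Spontaneous 2 (sudden cardiac death) | After 72 h | None | No | No |
| Spontaneous 3 (pathology) | After 72 h | None | No | No |

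**Counts.** Four of the six criteria name CK-MB and two need no biomarker. Two of the six need a normal baseline CK-MB, and these are both of the peri-procedural routes.

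**Other routes in the first 72 hours.** The two biomarker-free criteria belong to the spontaneous category, which starts after 72 hours. The post-surgery criterion requires cardiothoracic surgery. A CK-only subject who has had no such surgery therefore has no route to MI in the peri-procedural window.

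**Effect of *preferred*.** The word stands in the first peri-procedural route and in the post-surgery criterion, but not in the second peri-procedural route. It suggests that another post-procedure marker may be accepted, yet the visible text names none and gives no multiple for one. Even if another marker were accepted after the procedure, the condition of a normal baseline CK-MB would remain.

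**Size per subject.** Assume 85 subjects and no censoring before six months, so that the Kaplan-Meier rate equals the simple proportion. One subject whose only MAE is an unascertained peri-procedural MI then changes the rate by 1/85 = 1.2 percentage points. The total effect would be

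85 × m × f × (1 − o) subjects,

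where m is the true peri-procedural MI rate, f is the share of subjects with CK only (taken as unrelated to MI risk), and o is the share of affected subjects who already count through another MAE component. The documents give none of the three, so no total is calculated.

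**Context for the test.** Assume a one-sided 97.5% upper limit, in line with the 2.5% type I error in SAP Section 2.6, and again no censoring, so that Greenwood's formula reduces to the Wald form p + 1.96 × √(p(1 − p)/85).

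- 24 events: p = 28.2%, upper limit 37.8%, below the goal.
- 25 events: p = 29.4%, upper limit 39.1%, above the goal.

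With exact Clopper-Pearson limits, the largest passing count is 23 (27.1%, upper limit 37.8%). A single missed event would change the conclusion only if the true count lay just above one of these boundaries.

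**The case against.** **Adjudication could absorb the problem.** MAE is adjudicated by the CEC, and its manual (Section 8.1) and charter (Section 11.8.3) are not available here. They may hold a rule for missing baseline values. However, Section 11.8.3 also binds the committee to the definitions in the protocol. It would either apply them, so that CK-only subjects cannot qualify, or depart from them case by case. The possibility of an unseen rule stands. It does not reconcile the two protocol passages.

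**Parts of the protocol are not visible.** Table 2 and the procedure and post-procedure sections cannot be read, so the post-procedure enzyme schedule cannot be checked. A table note might require CK-MB. This limit stands. Section 6.1 nevertheless presents its list as following Table 2, and if the table said otherwise the two would themselves need reconciling.

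**The word *preferred* makes this an ambiguity rather than a bar.** That is fair for the post-procedure marker in the first route. It does not reach the baseline condition in either route.

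**Stronger readings that a reader might infer.** One is that every MI criterion needs CK-MB, so that MI as a whole is undetectable in CK-only subjects. Appendix II does not support this: two spontaneous criteria need no biomarker, and the post-surgery and first spontaneous criteria set no baseline condition. They need CK-MB around the event, and Section 6.1 governs only the baseline draw. Another is a definite loss of MAE events or percentage points. That would need an MI rate and a CK-only share, which the documents do not give. It would also have to allow for overlap, since a fatal infarction already counts as cardiovascular death.

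**Conclusion.** The point holds for peri-procedural MI only. Section 6.1 and the two peri-procedural criteria in Appendix II conflict. In a subject with CK alone at baseline, a component of the primary safety endpoint cannot be ascertained as defined during the first 72 hours, apart from the post-surgery route.

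The bias has a known direction, toward fewer MAEs, and an unknown size. It is zero if all sites draw CK-MB, and at most 1.2 percentage points for each affected subject, on the assumption of 85 subjects without censoring. Nothing in the documents shows that any site would use CK alone, or that the safety result would lie near the boundary.

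The conclusion rests on the visible text, on the definition being applied as written, and on no rule in Table 2 or the CEC documents that restores the missing baseline value. It is worth correcting because the remedy is small and a baseline sample that was not drawn cannot be recovered after the procedure.

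**What to change.** Reconcile the passages in one of two ways.

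1. Delete the CK option in Section 6.1, and in Table 2 if it is repeated there, so that CK-MB is collected at baseline and after the procedure.
2. If CK must remain at some sites, define in Appendix II the alternative marker that *preferred* implies, with its own threshold and its own baseline condition.

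In either case, state how the CEC classifies a subject whose baseline CK-MB is missing or abnormal. Removing the CK option does not settle this, because both routes presuppose a normal baseline value. The rule would also cover any subject already treated with CK only. Reporting how many treated subjects lacked a baseline CK-MB would give an upper bound on the number of subjects affected by the missing value.

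The cost is a short protocol amendment, a line in the CEC documents, and one routine assay in place of another. Sites that run only CK must change their lab order.

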6.5 Follow-up for All Subjects

Required clinical follow-up will be performed at the following intervals for all subjects with TVRS procedure attempt, regardless of whether a TVRS Clip was successfully implanted:

- Discharge post-TVRS procedure
- 30 days follow-up office visit (this visit must be conducted even if subject is in hospital)
- 6 months
 follow up office visit
- 1 year follow up office visit
- 2 years3 yearsfollow up office visitfollow up office visit
- Discontinuation

Follow-up visits will be calculated from the date of the Procedure. Follow-up assessments can be performed at any point in the window, and should be conducted, whenever possible, by the same individual who performed the baseline tests. The subject should be followed at the investigational site where the subject was enrolled, and may be followed at another investigational site only with prior agreement from that site's Investigator and from the Sponsor.

During the physical examination at the 30-day follow-up clinic visit, the implanting or treating investigator shall examine the integrity of the TVRS Clip. At the 30-day, 6-month, 1-year, 2-year and 3-year follow-up visits, all subjects must be examined by the Investigator. Subjects must continue to take baseline medications without change during follow-up, unless clinically (medically) necessary. If there are any cardiovascular medication changes (including dosage changes), these changes should be documented on the electronic case report form. In general, neurohormonal antagonists should not be changed. Subjects implanted with the TVRS Clip must also be evaluated for device integrity. Required tests and procedures outlined below must be completed. Timing of specific tests will follow the Clinical Evaluation Schedule (**Table 2**) outlined above. All visits and tests must be completed even if the subject is in hospital.

- 12-lead FCG
- Blood draw

(Version 2.0; 01 February 2018)

- Brief physical exam including vital signs (weight, heart rate, blood pressure and temperature)
- Echocardiogram TTE at all follow-up visits and TEE at 30-day visit only
- Modified Rankin Scale (Assessment of mRS should additionally be done at 90 days after onset of stroke)
- 6-Minute Walk Test (6MWT) (excluding discharge and 30-day follow-up visit) See
 APPENDIX VI for 6 Minute Walk Test Guidelines
- Concomitant cardiovascular medications assessment
- NYHA Functional Class assessment
- QoL questionnaires to be completed by the subject; Note: To minimize bias and undue influence, the QoL questionnaires will be completed by the subject, unless the subject is unable to complete the questionnaire on their own (a note to file must be completed to document the inability of subject to complete the questionnaire)
- Assess and record adverse events
- Assess and record protocol deviations

All subjects should continue to be monitored and treated per applicable standards of care consistent with the subject's condition. All subjects must be followed by the heart failure specialist investigator at all scheduled follow-up visits. The site Principal Investigator should collaborate with the other site investigators as applicable in determining the treatment strategy for all subjects enrolled at their site. The electronic case report forms will document changes in treatment strategy (i.e. new use of CRT, PCI, tricuspid valve surgery, and/or mitral valve surgery) and who was involved with determining changes in treatment strategy. Subjects implanted with the Clip must be evaluated for device integrity.

Additional subject visits may occur as clinically warranted. The following information must be collected as applicable:

- Adverse events
- Concomitant Cardiovascular Medications
- Hospitalizations
- Tricuspid valve surgery
- Additional TVRS procedure(s)

6.7 Additional Interventions for TR Reduction

It may be necessary for a subject to undergo additional interventions for TR reduction, such as an additional TVRS procedure or tricuspid valve surgery.

Requirements for this visit are as follows:

12-lead ECG

(Version 2.0; 01 February 2018)

- Blood draw (Note: if serum creatinine is elevated by at least 0.5 mg/dl on any visit compared to the prior visit or to baseline, an additional serum creatinine must be obtained between 30 and 45 days later to determine whether the increase is persistent)
- Weight, temperature, blood pressure and heart rate
- Transthoracic Echocardiogram (TTE)
- Concomitant cardiovascular medications assessment
- Assess and record adverse events
- Assess and record protocol deviations

Other scheduled follow-up visits from the date of the initial TVRS procedure must be conducted.

[figure not shown]
6.8 Heart-Related Office Visits

A Heart-Related Office Visit eCRF should be completed if a subject is seen for a heart related reason at the investigational site or at any other facility. Information pertaining to adverse events, heart failure medication changes or hospitalizations, as appropriate, should also be collected.

If an echocardiographic imaging study is performed at any visit, whether or not it is a study related visit, echocardiography images should be submitted to the ECL in a timely manner.

6.9 Tricuspid/Mitral Valve Surgery

Tricuspid and/or mitral valve surgery should not be performed during the follow-up period, unless deemed necessary by the site investigator(s). Tricuspid and/or mitral valve surgery will be considered a protocol deviation, unless the subject experiences a complication (e.g., endocarditis, clip detachment or leaflet injury) from the TVRS procedure. Subjects who undergo tricuspid and/or mitral valve surgery will continue to be followed per this Clinical Protocol.

(Version 2.0; 01 February 2018)

6.10 Explanted TVRS Clip

The TVRS Clip may be explanted during tricuspid valve surgery or an autopsy. If possible, fluoroscopic images with side views of the device should be obtained prior to explant. Following explant of the TVRS Clip(s) during surgery, the subject will continue to be followed as defined in **Section 6.4: Follow-up for All Subjects**. Explant information will be captured on the tricuspid Valve Surgery Form or Death Form.

7.0 ADVERSE EVENTS

To comply with worldwide standards and guidelines on clinical trial adverse event reporting, Abbott has developed uniform and worldwide applicable standard definitions and reporting timelines to be used and adhered to by the investigators.

7.1 Definitions

7.1.1 Adverse Event

An adverse event (AE) is any untoward medical occurrence, unintended disease or injury, or untoward clinical signs (including abnormal laboratory findings) in subjects, users or other persons, whether or not related to the investigational medical device.

- **Note 1:** This definition includes events related to the investigational medical device.
- Note 2: This definition includes events related to the procedures involved.

Note 3: For users or other persons, this definition is restricted to events related to investigational medical devices.

An AE can therefore be any unfavorable and unintended sign (including an abnormal laboratory finding), symptom, or disease temporally associated with the use of a medicinal (investigational) product, whether or not related to the medicinal (investigational) product.

